9.2.4 Participant Follow-up

For the vaccinated and concurrent control arms, study participants will be followed from the index date to the end of the study, loss to follow-up (deregistration), vaccination (for unvaccinated controls), vaccination of the matched control (for vaccinated people), or death, whichever is earlier.

9.3 Variables and Epidemiological Measurements

9.3.1 Exposures

The main exposure in this study is whether an individual was vaccinated with one, two or more doses of the Oxford/AstraZeneca COVID-19 or other COVID-19 vaccine. This includes next generation vaccines, if and when available. People without record of any COVID-19 vaccination are considered unexposed.

COVID-19 vaccination will be retrieved from the National Immunization Management System (NIMS), which contains detailed information on name of the COVID-19 vaccines, specific date of vaccination, and dose sequence (1st, 2nd or booster dose) of the injection given to each vaccinated individual.

Persons will be considered vaccinated with:

- one dose: from at least 22 days after dose 1 until the day before dose 2
- two doses: from at least 15 days after dose 2 until the day before a third dose
- additional doses: from at least 15 days after the previous dose, until the day before the subsequent dose

A subject is considered to have heterologous dosing after receipt of at least one dose of Oxford/AstraZeneca COVID-19 vaccine and at least one dose of another COVID-19 vaccine.

Variables	Categories	Data source	Comments
COVID-19 vaccine	-Oxford/AstraZeneca -Pfizer -Moderna	COVID-19 vaccination event from NIMSCollected daily batch from TRI week lag time	Collected daily, weekly batch from TRE; 1 week lag time
Date of vaccination	Specific date		
Dose number	1 st , 2 nd or booster dose		
Batch number			

Table 4. Exposure variables and data sources

NIMS: National Immunization Management System; TRE: trusted research environment

Vaccinated persons will be further stratified by time period after each dose and interval between doses.

9.3.2 Outcomes

The primary outcomes of this study are

- COVID-19 related hospitalization
- COVID-19 related ICU admission
- COVID-19 related death

The secondary outcomes of this study are

- All-cause hospitalization
- All-cause ICU admission
- All-cause mortality

The RAVEN extension outcomes are:

- Any positive SARS-CoV-2 test
- Medically attended COVID-19
- Emergency department visit associated with COVID-19
- HCRU (including but not limited, primary care consultations, prescriptions, medical tests and investigations; hospital outpatient attendances and procedures; hospital emergency department attendances without admission; hospital admissions) and associated cost related to COVID-19 and long COVID
- Breakthrough case
- Time to vaccine waning
- Long COVID (e.g. based on code for long COVID, on combination of code for long COVID and a positive SARS-CoV-2 test, on referral to long COVID clinic)
- A COVID-19 related event (GP attendance, accident department, hospitalization, ICU admission, death) is defined as:

- A medically attended event "Acute symptomatic COVID" defined as a positive test plus a clinical diagnosis or symptom (e.g. anosmia) which makes COVID plausible
- An emergency department attendance
- An event with an ICD-10 diagnosis of COVID-19
- An event within 28 days of a positive RT-PCR for SARS-CoV-2 infection or
- A visit with a patient presenting with respiratory symptoms or other symptoms credibly associated with COVID-19 within 28 days of a positive RT-PCR for SARS-CoV-2 infection.
 - Events within 14 days will feature in a sensitivity analysis.

Events of interest are those occurring between the index date and the end of follow-up. Only the first outcome event will be considered in the primary and secondary VE analysis.

The Hospital Episode Statistics (HES), Secondary Uses Service (SUS), General Practice Extraction Service data for pandemic planning and research (GDPPR), and Office of National Statistics (ONS) data may include information on COVID-19 infection through specific COVID-19 diagnosis codes. Using a combination of both COVID-19 SGSS/NPEX and diagnosis codes from HES, SUS, GDPPR, and ONS allow capturing the COVID-19 infection status for all study participants. Since testing for COVID-19 and its capture was not complete at the beginning of the pandemic but significantly improved later, restriction of the study period from July 2020 or the 2nd wave of infection by regions in England, whichever is later, for determining COVID-19 related events in the historical population is needed. Medically attended COVID-19 will come from ORCHID, GDPPR, Emergency Care Data Set (ECDS) and HES. Emergency department visits will come from ECDS. SARS-CoV-2 variants will come from COG UK. Data on HCRU and associated cost will come from HES using the Health Resource Grouper (HRG) and primary care attendance and medication costs. Long COVID will come from ORCHID and HES.

|--|

Variables		Data source	Comments
Hospitalization	Date	HES for curated data	6-8 weeks lag for HES
	Frequency	SUS for more recent raw data	SUS is updated weekly
	Duration	HES APC for combined	with a maximum of 2 weeks lag
ICU admission	Date	CC for ICU specific data	
	Frequency		
	Duration		
Death	Date	ORCHID/GDPPR for date	2 weeks lag
	Cause of death	ONS for cause of death	6 weeks lag
Medically attended COVID-19		ORCHID, GDPPR, ECDS, HES	
COVID-19 infection	Positive RT-PCR test; date	SGSS for first positive test in hospital and community NPEX for all positive/negative test in the community	Daily update
	ICD-10/SNOMED codes for COVID	HES, ONS, GDPPR	
SARS-CoV-2 variants of interest		COG UK	
Long COVID		ORCHID, HES	
HCRU and cost		HES & HRG	
		ICU datasets	
		Primary care attendance & costs	

APC: Admitted Patient Care; CC: Critical Care COG UK: COVID Genomics UK Consortium; ECDS: Emergency Care Data Set; GDPPR: General Practice Extraction Service data for pandemic planning and research; HES: Hospital Episode Statistics; HRG: Health Resource Grouper; ICU: Intensive Care Unit; NPEX: National Pathology Exchange; ONS: Office for National Statistics; ORCHID: Oxford-Royal College of General Practitioners Clinical Informatics Digital Hub; SGSS: COVID-19 Second Generation Surveillance System; SUS: Secondary Uses Service.

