- To conduct an analysis of COVID-19 and long COVID HCRU and health care	- HCRU for COVID-19
cost for the whole population and for risk groups identified as having a	- HCRU for long COVID
suboptimal vaccine response.	- healthcare cost for COVID-19
	- healthcare costs for long COVID
- To explore vaccine effectiveness against COVID-19 due to different SARS-	Same as primary objective
To assess the effectiveness of the Oxford/AstraZeneca COVID-19 vaccine against	-Any positive SARS-CoV-2 test
To assess the effectiveness of the Oxford/AstraZeneca COVID-19 vaccine against any positive SARS-CoV-2 test, medically attended COVID-19 and emergency	-Any positive SARS-CoV-2 test -Any medically attended COVID-19
To assess the effectiveness of the Oxford/AstraZeneca COVID-19 vaccine against any positive SARS-CoV-2 test, medically attended COVID-19 and emergency department visit associated with COVID-19.	-Any positive SARS-CoV-2 test -Any medically attended COVID-19 -Emergency department visit associated with COVID-19
 To assess the effectiveness of the Oxford/AstraZeneca COVID-19 vaccine against any positive SARS-CoV-2 test, medically attended COVID-19 and emergency department visit associated with COVID-19. To assess the effectiveness of the Oxford/AstraZeneca COVID-19 vaccine and other COVID-19 vaccines in people vaccinated with booster/other additional doses. 	-Any positive SARS-CoV-2 test -Any medically attended COVID-19 -Emergency department visit associated with COVID-19 Same as primary objective
 To assess the effectiveness of the Oxford/AstraZeneca COVID-19 vaccine against any positive SARS-CoV-2 test, medically attended COVID-19 and emergency department visit associated with COVID-19. To assess the effectiveness of the Oxford/AstraZeneca COVID-19 vaccine and other COVID-19 vaccines in people vaccinated with booster/other additional doses. To assess the effectiveness of heterologous dosing (including at least one Oxford/AstraZeneca COVID-19 vaccine) 	-Any positive SARS-CoV-2 test -Any medically attended COVID-19 -Emergency department visit associated with COVID-19 Same as primary objective Same as primary objective

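### The definition of a COVID-19 related event in section 9.3.2 includes an emergency department attendance with no COVID-19 condition, which contradicts the named ED outcome and, read literally, dilutes its VE

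*Protocol*

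**What the plan says.** Protocol section 9.3.2 introduces one shared definition: "A COVID-19 related event (GP attendance, accident department, hospitalization, ICU admission, death) is defined as". Five items follow:

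1. A medically attended event, "defined as a positive test plus a clinical diagnosis or symptom (e.g. anosmia) which makes COVID plausible".
2. "An emergency department attendance".
3. "An event with an ICD-10 diagnosis of COVID-19".
4. "An event within 28 days of a positive RT-PCR for SARS-CoV-2 infection or".
5. A visit with respiratory or other credible symptoms within 28 days of a positive RT-PCR.

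A 14-day window is kept for a sensitivity analysis.

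The outcome that item 2 bears on is listed among the extension outcomes in the same section as "Emergency department visit associated with COVID-19". Extension objective 4 in the synopsis uses the same description, "emergency department visit associated with COVID-19", and Table 3 repeats it. On data, section 9.3.2 says only this: "Emergency department visits will come from ECDS".

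**The concern.** Item 2 is the only one of the five with no test, diagnosis, symptom or time window. The items read as alternatives, so a fracture seen in an emergency department would qualify as a COVID-19 related event. That is not the outcome the protocol names. Nor is all-cause ED attendance a listed VE outcome: the all-cause outcomes are hospitalization, ICU admission and mortality.

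The estimate for objective 4 is at stake. Visits unrelated to COVID-19 carry no direct vaccine effect, so including them pulls VE away from its true value and toward whatever difference in general ED use exists between vaccinated and unvaccinated people. The large national dataset does not help. It narrows the interval around the wrong quantity.

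**Working it through.** **Text check.** Item 1 needs a positive test plus a diagnosis or symptom. Item 3 needs an ICD-10 COVID-19 diagnosis. Items 4 and 5 need a positive RT-PCR within 28 days. Item 2 needs nothing. The data-source text in section 9.3.2 names ECDS for ED visits and adds no restriction. Its list of sources for COVID-19 diagnosis codes is HES, SUS, GDPPR and ONS, and ECDS is not among them. Nothing elsewhere in the protocol supplies the missing condition.

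**Is item 2 needed?** The stem already names the accident department as an event type. An ED visit with a COVID-19 code meets item 3, and one within 28 days of a positive RT-PCR meets item 4. So item 2 either adds nothing or admits every other ED visit.

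**Size.** The protocol gives no ED event rate, COVID-19 share or expected VE for ED visits, so there is no figure to reproduce. All inputs below are assumptions, except that VE = 1 - RR (section 9.7.1).

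- f: COVID-19 share of first ED events in unvaccinated controls.
- VE: true effectiveness against COVID-19 ED visits.
- RR_non: vaccinated to unvaccinated rate ratio for non-COVID ED visits.

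Formula: RR_obs = f × (1 - VE) + (1 - f) × RR_non, and VE_obs = 1 - RR_obs.

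With RR_non = 1 this reduces to VE_obs = f × VE:

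| f | VE 60% | VE 80% | VE 90% |
|---|---|---|---|
| 5% | 3.0% | 4.0% | 4.5% |
| 10% | 6% | 8% | 9% |
| 30% | 18% | 24% | 27% |
| 50% | 30% | 40% | 45% |

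With unequal non-COVID ED use, f = 5% and VE = 80%:

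- RR_non = 0.9: RR_obs = 0.05 × 0.2 + 0.95 × 0.9 = 0.010 + 0.855 = 0.865, so VE_obs = 13.5%.
- RR_non = 1.1: RR_obs = 0.010 + 1.045 = 1.055, so VE_obs = -5.5%.

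As f falls, VE_obs tends to 1 - RR_non. If only COVID-19 ED visits count, f = 1 and VE_obs equals VE.

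**The case against.** The best defence is that nobody would program it this way. The outcome is named as COVID-specific wherever it appears. The list seems to mix event types with criteria, and nesting may have been lost when the text was extracted. The ENCePP checklist in Appendix B (item 6.2) also defers outcome definitions to the SAP, which was not available for this review. This lowers confidence that the analysis would in fact count all ED visits. It does not clear the text. Section 9.3.2 does give a definition, that definition contradicts the outcome's name, and if item 2 is only an event type it repeats the stem.

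A reader might infer more than the protocol supports, in three ways:

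- *VE collapses to zero.* This needs a small f, which the protocol does not state, and equal non-COVID ED use in both arms. At f = 50% VE is halved, not abolished. Section 9.11.1 itself allows that people who chose vaccination may differ from those who did not, so the limit need not be zero.
- *Medically attended COVID-19 has the same fault because it also draws on ECDS.* It has its own condition, a positive test plus a diagnosis or symptom, and naming ECDS as a source does not remove that.
- *The primary outcomes are affected because an admission through the ED would qualify.* The shared list leaves room for this misreading, but nothing in the protocol says that route of admission qualifies an event. Section 9.3.2 keeps all-cause hospitalization, ICU admission and mortality as separate outcomes.

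**Conclusion.** The point stands as a wrongly stated rule for one extension outcome. The ED item lacks the COVID-19 condition that the other four items have, and it contradicts the outcome it is meant to define. Followed literally, it dilutes VE for ED visits and draws the estimate toward 1 - RR_non. At an assumed true VE of 80%, measured VE is 4% to 40% for f from 5% to 50% with equal non-COVID ED use. At f = 5% its sign can turn on a 10% difference in that use. These sizes rest on assumed f, VE and RR_non and on the literal reading. They do not extend to medically attended COVID-19 or to the three primary outcomes.

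**What to change.** In section 9.3.2, do one of the following:

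- Delete the ED item, since the stem together with the ICD-10 and 28-day RT-PCR items already covers COVID-19 ED visits.
- Keep it with a condition attached: a COVID-19 diagnosis code where the ED data carry one, or a positive RT-PCR within 28 days, with 14 days in the sensitivity analysis. The qualifier on coding matters because the protocol does not list ECDS as a source of COVID-19 diagnosis codes.

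In either case, set out event types and qualifying criteria as two separate lists. State that each event type, including hospitalization, ICU admission and death, must meet a test or diagnosis criterion. This also removes the possible misreading for the primary outcomes. The SAP definition should be checked against the revised text.

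The cost is a few lines of protocol text and fewer counted ED events. The remaining events will not all be caused by COVID-19: an incidental visit, such as an injury within 28 days of a positive test, still counts. The 14-day sensitivity analysis gives some indication of how much that matters.

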Summary tables of all patient characteristics and end points indicated in section 9.3.2 will be created for both the before and after matching situation to provide insight in population characteristics as well as in errors and missingness. Categorical variables will be checked on meaningful categories and frequencies. It is not anticipated that categories will have too low frequency. Pooling will be considered when the frequency for a category becomes below 1000.

Continuous variables will be summarized in terms of min, max, interquartile range, median and mean to get insight in these variables, but also to provide a first indication of use of same unit across the database and to obtain a first impression about possible transformations needed. Missing values will be considered in detail. If the percentage of missingness is below 10%, complete case analyses will be performed. When exceeding 10%, multiple imputation will be run additionally based on the total dataset.

For each outcome event, the summary tables will present for each study cohort the number of first events, total person-years for the event and number of first events per person-years (rate), the RR and the VE which is calculated as 1 - RR. This will also be provided per age group and per frailty score where further stratification/subgroups are indicated below. Finally, VE will also be provided in shorter periods after dose 1, and between the doses, and presence of comorbidities.

Poisson regression with offset for time at risk will be used to estimate rates using the matched dataset, adjusting for the matching variables and BMI, smoking, prescribed medications, and frailty score, which are known to increase risk of hospitalization and death and are likely associated with vaccination.

Checks on linearity for continuous variables will be performed. In order to evaluate interactions of independent variables with the exposure (i.e. vaccinated/comparator), continuous variables will be categorized and the VE will be tabulated per category. For variables for which the maximum and minimum VE across categories is more than 10% different, interaction effects with the exposure will be taken into account in the Poisson model. For interactions among independent variables that are not the exposure, interaction variables will be created. Forward selection is performed, and interaction variables will be included when the computed VE changes with more than 10%.

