9.7.3 Sensitivity Analyses

Several sensitivity analyses will be considered

- Only HES data are included for follow-up data on hospitalization and ICU-admission
- People with history of COVID-19 infection prior to vaccination not excluded from the study population
- A COVID-related event within 14 days of a positive RT-PCR for SARS-CoV-2 infection.
- Addition of the following exclusion criterion: People whose household had more than 10 people with an average age of 65 years and over. This is a proxy for people living in an elderly care home (and only available for a subset of ORCHID data). They will generate a strong confounding effect of (due to the targeted vaccination of these residents and their high risks of COVID-19-related events) and the lack of available controls.

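### The primary COVID-19 outcomes count any-cause events within 28 days of a positive RT-PCR, with the order of test and event left open, so incidental events can lower VE against severe disease

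*Protocol*

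**What the plan says.** Section 9.3.2 introduces the definition with "A COVID-19 related event (GP attendance, accident department, hospitalization, ICU admission, death) is defined as" and then lists alternative criteria. Three matter here:

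- the test criterion, "An event within 28 days of a positive RT-PCR for SARS-CoV-2 infection or";
- the diagnosis criterion, "An event with an ICD-10 diagnosis of COVID-19";
- the symptom criterion, "A visit with a patient presenting with respiratory symptoms or other symptoms credibly associated with COVID-19 within 28 days of a positive RT-PCR".

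The test criterion ends in a connective that makes the next item an alternative. Neither the diagnosis item nor the symptom item is a condition on it.

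The same section states that "Only the first outcome event will be considered in the primary and secondary VE analysis". Table 5 gives the test source as "SGSS for first positive test in hospital and community", so swabs taken during a stay are in the data. Table 5 also lists ONS cause of death, but the test criterion does not use it.

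The one related check is in section 9.7.3: "A COVID-related event within 14 days of a positive RT-PCR for SARS-CoV-2 infection". All-cause hospitalization, ICU admission and mortality are separate secondary outcomes. The limitations in section 9.9 mention missed infections and misdiagnoses, but not incidental or hospital-acquired cases.

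**The concern.** The primary objective is VE against severe COVID-19. As written, the rule brings in events of another kind: an elective admission, or a death from an unrelated cause, within 28 days after a mild or screening positive. How often these occur depends on how often people are infected and how often they are admitted or die anyway. Their rate ratio therefore follows VE against infection, and mixing them in pulls the primary estimate that way.

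The open direction adds a second route. If the window is also read backwards, a person admitted for a fracture who first tests positive on day 20 of the stay is a COVID-19 hospitalization, dated before the infection. Section 9.7.2 plans mostly 7-day bands after dose 1, so such an event could sit up to 28 / 7 = 4 bands too early.

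Because only the first event counts, an incidental admission can also take the place of a later admission caused by COVID-19.

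**Working it through.** **The criteria side by side.** An event qualifies if any one criterion is met. A visit with compatible symptoms within 28 days of a positive test is already an event within 28 days of a positive test. On a literal reading the symptom criterion neither adds nor excludes anything. The 14-day analysis changes the length of the window and sets neither an order nor a cause.

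**What each reading of the window lets in**

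| Event | Forward only | Both directions |
|---|---|---|
| Any-cause admission, ICU stay or death after a positive | counts | counts |
| Admission for another reason, first positive later in the stay | not by the test criterion | counts |
| ICU admission or death after a hospital-acquired positive | counts | counts |

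A hospital-acquired case that is coded with COVID-19 during the stay qualifies under either reading through the diagnosis criterion, which has no timing or position condition.

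**Effect on VE.** The protocol gives no event count, incidental share or dilution figure, so there is nothing of its own to reproduce. Section 9.7.1 sets the measure: "the RR and the VE which is calculated as 1 - RR". Let f be the share of control-arm qualifying events that are incidental or hospital-acquired. Then

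RR_obs = (1 − f) × RR_severe + f × RR_incidental, and VE_obs = 1 − RR_obs.

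The loss in VE is f × (RR_incidental − RR_severe).

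Inputs:
- Section 7 quotes trial efficacy of 82% against symptomatic infection and 100% against severe infection. Used as stand-ins, these give RR_incidental = 0.18, RR_severe = 0 and a loss of 0.18 × f.
- All values of f are assumptions. So are the VE values in the last two columns.

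| f | Protocol's figures (100% / 82%) | Assumed 90% / 50% | Assumed 90% / 20% |
|---|---|---|---|
| 10% | 98.2% | 86% | 83% |
| 20% | 96.4% | 82% | 76% |
| 40% | 92.8% | 74% | 62% |

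For example, 1 − (0.8 × 0.10 + 0.2 × 0.50) = 0.82.

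If the two VE values are about equal, nothing is lost. With RR_severe = 0.20 and RR_incidental = 0.18, VE_obs runs from 80.0% at f = 0 to 81.0% at f = 50%.

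**Effect of the window.** Let b be the background admission rate per person-year, h the risk of a COVID-caused admission per infection, and w the window in days. Then f = (b × w / 365.25) / (b × w / 365.25 + h), with h held fixed as w changes. Both b and h are assumptions. The central case is b = 0.2 and h = 5%; the range covers b from 0.1 to 0.4 and h from 2% to 10%.

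| Window | f, central case | f, range | VE on the protocol's figures, central case |
|---|---|---|---|
| 14 days, one direction | 13.3% | 3.7% to 43.4% | 97.6% |
| 28 days, one direction | 23.5% | 7.1% to 60.5% | 95.8% |
| 28 days, both directions (56 days) | 38.0% | 13.3% to 75.4% | 93.2% |

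Leaving the direction open therefore matters, and halving the window lowers the incidental share without bringing it to zero.

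**The case against.** The strongest reply has four parts.

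1. **Direction.** A reader might infer that the protocol adopts a two-sided window. It does not say so. The wording allows it by silence, and many would read the phrase as an event following a test. On that reading the fracture example drops out of the test criterion, and for deaths the backward direction is close to empty. This part stands: the direction is under-specified, not shown to be wrong.
2. **Deferral.** The ENCePP checklist (item 6.2) leaves the definition of outcomes to the SAP, which may set the order of test and event. That is fair for direction. It is weaker for the any-cause rule, which section 9.3.2 states outright, and section 9.7.1 says that major changes to primary endpoint definitions would be reflected in a protocol amendment. The checklist also answers no on analytic control of outcome misclassification (item 10.6).
3. **Breadth is deliberate.** Section 9.3.2 combines tests and codes so that infection status is captured for all participants. A broad definition finds cases that coding misses. That supports keeping it, but not leaving it without a specific counterpart.
4. **Existing checks.** The 14-day analysis is a partial check, so it would be too strong to call it no check at all. The all-cause outcomes do not isolate cause.

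A reader might also infer a known distortion across age and comorbidity groups, since older and sicker people are admitted more often. The documents do not establish it. In the window formula f depends only on the ratio b/h: b = 0.2 with h = 5% and b = 0.4 with h = 10% both give 23.5%. If background and causal risk rise together, the share need not change.

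**Conclusion.** The point holds as a weakness in how the protocol words its primary outcomes. Any-cause events after a positive test count under every reading. Hospital-acquired admissions count through the test criterion only if the window runs both ways, though they may still enter through an ICD-10 code.

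The bias is downward provided that VE against infection is below VE against severe disease. The efficacy figures in section 7 support that ordering, but they are trial figures for symptomatic infection, not VE against any positive test. The size is not derivable from the documents. It is 1.8 points at a 10% incidental share and 7.2 at 40% on the protocol's figures, and 4 to 28 points over the same shares on the lower VE values assumed above. These figures are illustrations and do not forecast the result. The case for acting is that the change is cheap and bears directly on what can be concluded about severe disease.

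**What to change.** 1. **Section 9.3.2.** State the direction of the window. For hospitalization and ICU admission, the qualifying positive should fall before admission or within a short, prespecified interval after it. For death, it should fall before or at death. Tabulate admissions first positive later in the stay separately, as hospital-onset. Apply this to the ICD-10 criterion as well as the test criterion; otherwise a coded hospital-acquired case still enters. Delete the symptom criterion or reword it so that it has an effect.
2. **Section 9.7.3.** Add a sensitivity analysis that counts only admissions with COVID-19 as the primary ICD-10 diagnosis (HES) and deaths with COVID-19 as certified cause (ONS). Keep the broad 28-day definition for comparison. The gap between the two results would show how much incidental events matter.

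The cost is a wording change and one more run on HES, SGSS and ONS data, all already listed in section 9.4. The restricted analysis will have fewer events and will lose some true cases that were tested late or coded secondarily, so it should be read beside the broad definition and not replace it.

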The UK was one of the first countries that introduced a mass vaccination campaign for COVID-19 and first started vaccinating the elderly population (JCVI, 2020). Three COVID-19 vaccines were licensed and are being used including the Moderna, the BioNTech/Pfizer, and the Oxford/AstraZeneca vaccines. Vaccination with the BioNTech/Pfizer vaccine started in December 2020 and with the Oxford/AstraZeneca vaccine started in early January 2021. The need for booster COVID-19 vaccination was anticipated (Mahase, 2021) and it was introduced in the UK in September 2021. This study is to primarily assess the effectiveness of the Oxford/AstraZeneca COVID-19 vaccine. Given the known high efficacy of the mRNA vaccine in clinical trials and real-world studies, the study is also to evaluate the VE of other COVID-19 vaccines as a validation of the study's methods.

Whist some early studies have been conducted little is known about the health economic impact of COVID-19 vaccination. There have been exploratory studies of the impact of vaccination on disease transmission and the health-economic impact of COVID-19 (HM Government, 2020; Sandmann et al, 2021).

A further challenge in the management of people with COVID-19 has been the emergence of long COVID. This has been quite disabling for a large number of people. However, clinical terms to record long COVID in clinical records were created late, so data quality of cases in clinical records is suboptimal (Crook et al, 2021; Mayor, 2021).

8. **OBJECTIVES**

The study's primary objective is to assess the overall effectiveness of at least one dose of the Oxford/AstraZeneca COVID-19 vaccine by number of doses, by age groups, by comorbidity status, by time periods after each dose and by interval between the doses. The secondary objective is to assess the overall effectiveness of at least one dose of other COVID-19 vaccines, by number of doses, by age group, and by time periods after each dose, intervals between doses, and comorbidities that are known to associated with more severe COVID-19 infection and/or suboptimal response to the vaccine.

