9.2 Setting

9.2.1 Study Population

The study population of this study is people in England who have received at least one dose of the Oxford/AstraZeneca COVID-19 vaccine from January 2021 onwards (the AstraZeneca vaccine arm) or at least one dose of another (e.g. mRNA) COVID-19 vaccine from December 2020 onwards (the Other vaccine arm) and people in England who were not vaccinated with any COVID-19 vaccine during the same time period (concurrent control arm) who will be matched to the vaccinated individuals by age, gender, GP practice (NHS region), and comorbidity (see Section

9.7.1 for a description of matching). Study participants of any age will be considered. For the vaccinated individuals, the study's index date is the date of vaccination of the 1st dose.

Concurrent controls who become vaccinated will be censored at date of vaccination and, then may re-enter the study as newly vaccinated individuals. An appropriate control group will be identified for the booster dose evaluation.

To contextualize, we will describe the impact of SARS-CoV2 on the unvaccinated English population, prior to the availability of COVID-19 vaccines. We will conduct a descriptive analysis of COVID-19 of this historical population of unvaccinated persons in England.

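### The protocol counts events from the day of dose 1 but counts a person as vaccinated only from day 22, and sets no start day for the overall VE of at least one dose

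*Protocol*

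**What the plan says.** Three sections put time zero at vaccination. Section 9.2.1: "For the vaccinated individuals, the study's index date is the date of vaccination of the 1st dose". Section 9.2.4: "study participants will be followed from the index date to the end of the study", with earlier stops that include vaccination of the matched control. Section 9.3.2: "Events of interest are those occurring between the index date and the end of follow-up", with only the first event used in the primary and secondary VE analyses. Section 9.7.1 then tabulates "the number of first events, total person-years for the event and number of first events per person-years (rate), the RR and the VE", and mentions no lag.

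Section 9.3.1 defines when a person is regarded as vaccinated. The first state is given as "one dose: from at least 22 days after dose 1 until the day before dose 2". For the next state the lag is shorter and is counted afresh: "two doses: from at least 15 days after dose 2 until the day before a third dose".

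These lags belong to dose-specific states. Section 8 makes the pooled contrast primary: "The study's primary objective is to assess the overall effectiveness of at least one dose of the Oxford/AstraZeneca COVID-19 vaccine". Section 9.7.2 lists that contrast again as a possible stratum. No section gives its start day.

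**The concern.** Both the event window and the exposure window are written down, and they disagree. Under the event window, a hospital admission on day 10 after dose 1 is a first event in the vaccinated arm. Under the exposure rule, that person is not yet vaccinated with one dose. Two analysts following the same protocol could report different overall VEs for COVID-19 hospitalization, ICU admission and death.

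The early window may carry a lot of weight, because a vaccinated person's follow-up ends when the matched control is vaccinated. Where uptake was fast, many pairs stop soon after day 21. The weight of the early window then varies with control uptake. Differences in VE between age bands could appear with no difference in vaccine effect, if those breakdowns use the unlagged exposure.

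**Working it through.** **Design figure.** The protocol gives no expected VE, event count or follow-up length, so there is none to reproduce. What follows is an illustration.

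**Windows side by side.**

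| Period | 9.2.1, 9.2.4, 9.3.2 | 9.3.1 |
|---|---|---|
| Days 0-21 after dose 1 (22 days) | events and time count | not yet one dose |
| Day 22 to the day before dose 2 | count | one dose |
| Days 0-14 after dose 2 (15 days) | count | in no dose state |
| Day 15 after dose 2 onward | count | two doses |

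**Inputs from the protocol (section 9.5).** Coverage c with any vaccine by 7 April 2021 was 91% at age 65+ (the same figure is given for 65-79 and 80+) and 42.1% overall.

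**Assumptions.**
- Control vaccination follows a constant hazard that reproduces c over T days.
- T is 98 days (14 weeks, from early January, the start of the Oxford/AstraZeneca vaccine) or 120 days (about 17 weeks, from 8 December 2020, the start of matching).
- A pair is followed for up to T days and ends only when its control is vaccinated.
- Incidence is flat.
- True VE from day 22 is 80%.
- Apparent VE on days 0-21 is 0%, 30% or 90%.

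**Step 1: hazard.** h = -ln(1 - c)/T. For T = 98:
- 65+: 2.408/98 = 0.0246 per day, a mean of about 41 days.
- All ages: 0.5465/98 = 0.00558 per day, a mean of about 179 days.

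**Step 2: share of pair-time on days 0-21.** f = (1 - exp(-22h))/(1 - exp(-Th)). The denominator equals c.

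| | T = 98 days | T = 120 days |
|---|---|---|
| 65+ | (1 - 0.5824)/0.91 = 0.459 | (1 - 0.6431)/0.91 = 0.392 |
| All ages | (1 - 0.8846)/0.421 = 0.274 | (1 - 0.9047)/0.421 = 0.226 |

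**Step 3: overall VE counted from day 0.** With flat incidence, overall VE = f × early VE + (1 - f) × 0.80. For T = 98:

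| Early VE | 65+ | All ages |
|---|---|---|
| 0% | 0.541 × 0.80 = 43% | 0.726 × 0.80 = 58% |
| 30% | 0.138 + 0.433 = 57% | 0.082 + 0.581 = 66% |
| 90% | 0.413 + 0.433 = 85% | 0.247 + 0.581 = 83% |

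Counted from day 22 in both pair members, the result is 80% in every row by construction.

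**Step 4: dependence on follow-up length.** Give every pair the same follow-up of T days, so that f = 22/T, and set early VE to 0%. Take the 82% efficacy quoted in section 7 as the later VE. Then 82% becomes 22% at 30 days, 39% at 42 days, 72% at 180 days and 77% at 365 days. The loss runs from 60 points to 5.

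**The case against.** The strongest reply is that 9.3.1 already settles the matter. At least one dose can be read as the union of the one-dose, two-dose and additional-dose states. A person on days 0-21 is then in no vaccinated state, and 9.3.2 only sets the outer limits for finding events. That reading is tenable, so this is an unresolved contradiction and not a proven decision to count from day 0. It does not remove the problem, because 9.2.4, 9.3.2 and 9.7.1 say the opposite when read literally and nothing links them to 9.3.1.

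The early period is also partly covered. VE by time after each dose is part of the primary objective, and 9.7.1 promises VE in shorter periods after dose 1. The windows 0-7, 8-14 and 15-21 days in 9.7.2 are optional and limited to people with one dose only. These results would show the early period but would not correct a pooled figure. No sensitivity analysis in 9.7.3 starts at day 22.

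One could also leave the risk window to the SAP. That would be fair if the protocol were silent, but it states two windows that conflict.

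The limits on the numbers stand. Section 9.5 gives population coverage, not a hazard among matched controls, and the constant hazard is assumed. Projecting the 65+ hazard to a year is unsafe, because 9.1 expects the remaining unvaccinated to include people in terminal care or little engaged with the health system. Section 9.11.1 expects differences between those who choose vaccination and those who do not, so apparent early VE need not be zero.

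Starting at vaccination also has a real merit: it aligns time zero with matching. A day-22 start conditions on pairs that reach day 22.

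**Conclusion.** The contradiction is in the text and affects the first item of the primary objective, so the sections must be reconciled. Under the stated assumptions, days 0-21 would make up about 39-46% of pair-time at 65+ and 23-27% at all ages. Over 14 weeks, an 80% VE would read as 43% and 58% with no early effect, or 57% and 66% with an early VE of 30%.

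A reader might infer that the headline VE is certain to be heavily diluted. The documents do not support that. It is not settled that day 0 applies, no follow-up length is given, and an apparent early VE of 90% would lift the figure to about 85% and 83%. Nor do they show that the age and comorbidity breakdowns rest on the unlagged exposure, since the objectives list these in parallel with the overall estimate. They also do not show that the comparison with other vaccines is distorted. What is established is that the overall VE has two possible meanings, and that the gap between them can be large where pairs are short.

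**What to change.** In sections 9.3.2 and 9.7.1:
- State that, for the overall at-least-one-dose VE and any breakdown using that exposure, events and person-time start at day 22 after dose 1. Apply this to both members of pairs still event-free and uncensored at that point. It follows the exposure rule already in 9.3.1.
- State whether days 0-14 after dose 2 stay in the at-least-one-dose exposure, since 9.3.1 places them in no dose state.
- Report days 0-21 separately as a diagnostic window that is not part of the VE.
- Add the day-0 version to 9.7.3 as a named sensitivity analysis. If the sponsor prefers day 0 as primary, name that estimand and make day 22 the sensitivity analysis.

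The cost is a few sentences, fewer events, a somewhat wider confidence interval, and an estimate conditional on pairs reaching day 22. No new data are needed.
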